3.2. Patient Selection

3.2.1. Inclusion Criteria

All patients must satisfy the following criteria to be considered for study participation:

1. Patient and/or parent(s)/caregiver(s) fully comprehend the informed consent form (ICF) and assent form, understand all study procedures, and can communicate satisfactorily with the investigator and study coordinator, in accordance with applicable laws, regulations, and local requirements.
2. Males and females from 8-17 years of age, inclusive.
3. Genetically confirmed diagnosis of Prader-Willi Syndrome using standard DNA methylation test or fluorescent *in situ* hybridization. Documentation of genetically confirmed diagnosis of Prader-Willi Syndrome is acceptable.
4. A score of ≥ 10 on the HQ-CT.
5. A caregiver is available to complete the HQ-CT.
6. If female, is either not of childbearing potential (defined as premenarchal or surgically sterile [bilateral tubal ligation, bilateral oophorectomy, or hysterectomy]) or practicing one of the following medically acceptable methods of birth control:
 - a. Hormonal methods such as oral, implantable, injectable, vaginal ring, or transdermal contraceptives for a minimum of 1 full cycle (based on the patient's usual menstrual cycle period) before study drug administration.
 - b. Total abstinence from sexual intercourse since the last menses before study drug administration.
 - c. Intrauterine device.
 - d. Double-barrier method (condoms, sponge, or diaphragm with spermicidal jellies or cream).
7. Adequate renal function, defined as serum creatinine $\leq 1.5 \times$ upper limit of normal (ULN) and urine protein/creatinine ratio < 0.2 .
8. Adequate hepatic function, defined as total bilirubin $\leq 1.5 \times$ ULN and aspartate aminotransferase (AST) and Alanine aminotransferase (ALT) levels $\leq 3 \times$ ULN.
9. Growth hormone treatment will be permitted if doses have been stable for at least 1 month prior to screening.
10. Psychotropic treatment will be permitted and should be stable at least 6 weeks prior to screening.
11. Any other treatment including thyroid hormones should be stable for at least 6 weeks prior to screening.

3.2.2. Exclusion Criteria

Patients will be excluded for any of the following:

1. Known use of cannabis or cannabinoid-containing products for 4 weeks prior to baseline.
2. History of chronic liver disease, such as cirrhosis or chronic hepatitis due to any cause, or suspected alcohol abuse.
3. Use of weight loss agents or drugs known to affect appetite (including glucagon-like peptide-1[GLP-1] analogs) within 2 months prior to screening.
4. Uncontrolled Type I and Type II diabetes.
5. Currently taking concomitant medications that are strong cytochrome P450 3A4 (CYP3A4) or CYP2D6 inhibitors; or inducers of CYP3A4- or CYP2D6-sensitive substrates with a narrow therapeutic index.
6. Co-morbid condition or disease (such as respiratory disease, heart disease, or psychiatric disorder) diagnosed less than 1 month prior to screening.
7. History or presence of gastrointestinal or any other condition known to interfere with the absorption, distribution, metabolism or excretion of drugs as determined by the Investigator.
8. Patients who have participated in any other trials involving an investigational product or device within 30 days of screening or longer as required by local regulations.
9. Clinically significant abnormalities on ECG at screening or other evidence of heart disease as determined by the Investigator.
10. Has screening systolic blood pressure ≥ 160 mm Hg and diastolic blood pressure > 100 mm Hg (may be repeated one additional time after 5 minutes' rest to verify). Patients with hypertensive levels lower than those specified may be excluded at the Investigator's discretion if deemed to be in the best interest of the patient.
11. Currently taking felbamate.
12. Uncontrolled sleep apnea.
13. Pregnant or lactating female.
14. History of hypersensitivity to drugs with a similar chemical structure or class as CBD.
15. Unwillingness or inability to follow the procedures outlined in the protocol.
16. Patient judged by the investigator or sponsor (or designee) as unable to comply with the treatment protocol, including appropriate supportive care, follow-up and research tests.
17. Positive drug screen, including THC, at time of screening.
18. Creatinine clearance test of < 30 mL/min.

3.3. Removal of Patients from Therapy or Assessment

Patients will be allowed to discontinue their participation in the study at any time for any reason (withdrawal of consent). Furthermore, participation in this clinical study may be discontinued by the Investigator or by the sponsor for any of the following reasons:

- Intolerable side effects of the study product.

- Changes in medical status or medical condition of the patient such that the Investigator believes that patient safety will be compromised or that it would be in the best interest of the patient to stop treatment.
- Pregnancy.
- Relevant non-compliance with the protocol.
- Any use of marijuana, confirmed by a positive drug screen for THC.

In the event of a patient's withdrawal, the Investigator will promptly notify the sponsor. Every effort will be made to complete the end-of-study assessments.

Should any patient choose to withdraw early from the study, they will be advised of the safety precautions to be taken and will be followed until resolution of any AE or until the unresolved AEs are judged by the investigator to have stabilized.

Patients who are withdrawn from the study may be replaced at the discretion of the Sponsor.

3.4. Premature Patient Withdrawal

All patients will be advised that they are free to withdraw from participation in this study at any time, for any reason, and without prejudice. Every reasonable attempt should be made by the investigator to keep patients in the study. However, patients must be withdrawn from the study if they withdraw consent to participate. Investigators must attempt to contact patients who fail to attend scheduled visits by telephone or other means to exclude the possibility of an AE being the cause of withdrawal. Should this be the cause, the AE must be documented, reported, and followed as described in Section 6.2.6. The sponsor reserves the right to request the withdrawal of a patient due to protocol violations (i.e., terminating investigational product treatment and/or procedures) or other reasons.

The investigator also has the right to withdraw patients from the study at any time for lack of therapeutic effect that is intolerable or otherwise unacceptable to the patient, for intolerable or unacceptable AEs, intercurrent illness, noncompliance with study procedures, administrative reasons, or in the investigator's opinion, to protect the patient's best interest.

If a patient is withdrawn before completing the study, the reason for withdrawal and the date of discontinuation will be recorded on the appropriate case report form (CRF). Whenever possible and reasonable, the evaluations that were to be conducted at the completion of the study should be performed at the time of premature discontinuation.

3.5. Dose Adjustment Criteria

During the Maintenance Period, patients may have their dose of blinded study medication adjusted down to 30 mg/kg/day at the discretion of the Investigator or qualified designee based on the patient's tolerability. If the lower dose is not tolerated, the drug will be discontinued and the patient will be withdrawn from the study.

3.6. Stopping Rules

The Investigator reserves the right to terminate the study in the interest of patient safety and welfare. The Sponsor reserves the right to terminate the study at any time for administrative reasons. Patients will also be discontinued when their liver enzymes and serum bilirubin reach:

- ALT or AST > 8 x ULN
- ALT or AST > 5 x ULN for more than 2 weeks
- ALT or AST > 3 x ULN and (TU>2 x ULN or INR>1.5)
- ALT or AST > 3 x ULN with appearance of fatigue, nausea, vomiting, right upper quadrant pain or tenderness, fever, rash, and/or eosinophilia (> 5%)

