			TITRATION PERIOD ^a (1 Week)			MAINTENANCE PERIOD (12 Weeks)						
Visit Number	1	2	3 Baseline	Call/ Email	4	5	6	7	8	9	10 Study Completion / Early Withdrawal	11
Study Time Point	Week -4 to -2	Week -2	Day 1	Day 3 & 6	Day 7	Week 3	Week 5	Week 7	Week 9	Week 11	Week 13	Week 15
Visit Window (Days)	±3	±3	±3	0	0	±3	±3	±3	±3	±3	±3	±3
PROMIS Physical Activity and Fatigue pediatric short-form questionnaires			X			X			X		X	
Patient Global Impression of Severity (PGI-S)			X									
Patient Global Impression of Change (PGI-C)						X			X		X	
DEXA scan ^c			X								X	
Columbia Suicide Severity Rating Scale (C-SSRS)			X								X	
Review of concomitant medications	X	X	X	X	X	X	X	X	X	X	X	X
Review of adverse events	X	X	X	X	X	X	X	X	X	X	X	X
Pharmacokinetics ^c			X				X		X		X	

DEXA = Dual energy X-ray absorptiometry; PROMIS = Patient-Reported Outcomes Measurement Information System

^a Titration schedule = Days 1-3: 20 mg/kg/day; Days 4-6: 30 mg/kg/day; Day 7: 40 mg/kg/day. Phone calls will be made at Day 3 and Day 6 to determine if the patient’s dose may be titrated to the next dose level.

^b The Follow-up Visit is only for patients who do not choose to enroll in the long-term safety study and are tapering off the study drug. Patients will return to the site for assessment of concomitant medications, AEs, and to return and reconcile study drug.

^c Blood draws for trough pharmacokinetic analyses of CBD and metabolite 7-OH-CBD will be collected prior to morning dose at Visit 3 (Baseline) and Visit 6, 8, and 10 during the Maintenance Period.

^d Blood and urine samples for hematology, chemistry, and urinalysis will be collected at Screening (visit1), and Study Completion (Visit 10)/Early Withdrawal. Blood sample for complete blood count (CBC) will be collected at Week 3 (Visit 5).

^e DEXA scan will be completed on a subset of 20 patients.

TABLE OF CONTENTS

PROTOCOL APPROVAL PAGE	2
PROTOCOL SYNOPSIS	3
TABLE OF CONTENTS.....	14
LIST OF TABLES	19
LIST OF FIGURES	19
LIST OF ABBREVIATIONS AND DEFINITIONS OF TERMS.....	20
1. INTRODUCTION	23
1.1. Cannabidiol.....	23
1.1.1. Mechanism of Action	24
1.1.2. Metabolism and Potential Drug Interactions	24
1.2. Nonclinical Experience.....	24
1.2.1. Safety	24
1.2.2. Efficacy.....	25
1.2.2.1. Single Dose Regimens	25
1.2.2.2. Multiple Dose Regimens	26
1.3. Clinical Experience.....	26
1.3.1. Pharmacokinetics	28
1.3.2. Overview of Safety	29
1.3.3. Clinical Safety Data.....	29
1.4. Prader-Willi Syndrome.....	32

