In an open label study of Epidiolex[®] (a plant-derived purified CBD), 214 patients suffering from different refractory epilepsies were enrolled between January 15, 2014, and January 15, 2015 (Devinsky et al., 2016). Patients were given oral cannabidiol at 2-5 mg/kg per day, up-titrated until intolerance or to a maximum dose of 25 mg/kg or 50 mg/kg per day (dependent on study site), for a 12-week treatment period. Titration to a maximum dose of 50 mg/kg per day was done in 48 (30%) patients, 23 of whom received a dose of more than 25 mg/kg per day during the 12-week treatment period. Of the 214 enrolled patients, 162 (76%) patients who had at least 12 weeks of follow-up after the first dose of cannabidiol were included in the safety and tolerability analysis, 137 (64%) patients were included in the efficacy analysis.

The most common adverse events reported (in more than 10% of patients) were somnolence (n=41, 25%), decreased appetite (n=31, 19%), diarrhea (n=31, 19%), fatigue (n=21, 13%), and convulsion (n=18, 11%). Five (3%) patients discontinued treatment because of an adverse event. Serious adverse events were reported in 48 (30%) patients, including one death—a sudden unexpected death in epilepsy regarded as unrelated to study drug; 20 (12%) patients had severe adverse events possibly related to cannabidiol use, the most common of which was status epilepticus (n=9 [6%]).

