4.1.5. Taper Period

Following the completion of the Maintenance Period (Visit 10), patients will have the option to continue treatment in an open-label long-term safety study. Patients who choose to enroll in the long-term safety study will not have a follow-up visit. Patients who do not choose to enroll in the long-term safety study will taper the dose of study medication according to the following schedule: 40 mg/kg/day dose will be reduced to 30 mg/kg/day for three days, then 30 mg/kg/day will be reduced to 20 mg/kg/day for three days and then discontinued; 30 mg/kg/day dose will be reduced to 20 mg/kg/day for three days and then discontinued.

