6.2.5. Clinical Laboratory Assessments

6.2.5.1. Hematology

Blood samples for the following hematology assessments will be collected at the Screening (Visit 1), and Study Completion/Early Withdrawal (Visit 10) Visits: hemoglobin, hematocrit, total and differential leukocyte count, red blood cell (RBC), and platelet count.

6.2.5.2. A sample for complete blood count (CBC) will be collected at Week 3 (Visit 5).Chemistry

Blood samples for the following serum chemistry assessments will be collected at the Screening (Visit 1), and Study Completion/Early Withdrawal (Visit 10) Visits: albumin, blood urea nitrogen (BUN), creatinine, total bilirubin, alkaline phosphatase (ALP), aspartate transaminase (AST), alanine transaminase (ALT), sodium (Na⁺), potassium (K⁺), chloride (Cl⁻), lactate dehydrogenase (LDH), uric acid, glucose, and calcium.

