6.2.6. Adverse Events and Serious Adverse Events

6.2.6.1. Definition of Adverse Events

An AE is defined as any untoward medical occurrence in a patient administered a pharmaceutical product during the course of a clinical investigation. An AE can therefore be any unfavorable

and unintended sign, symptom, or disease temporally associated with the use of an investigational product, whether or not thought to be related to the investigational product.

Patients will be monitored throughout the study for AEs. Monitoring for treatment-emergent AEs (TEAEs) will begin as soon as the patient is dosed. All AEs must be followed until they are resolved or stabilized, or until all attempts to determine resolution of the event are exhausted. The investigator should use their discretion in ordering additional tests as necessary to monitor the progress of such events.

An AE may be:

- A new illness, not documented in the patient's medical history;
- Worsening of a concomitant illness;
- An effect of the study medication; it could be an abnormal laboratory value, as well as a significant shift from baseline within normal range which the qualified investigator or medical qualified designate considers to be clinically important;
- A combination of two or more of these factors.

Surgical procedures themselves are not AEs. They are therapeutic measures for conditions that require surgery. The condition for which the surgery is required is an AE, if it occurs or is detected during the study period. Planned surgical measures permitted by the clinical study protocol and the condition(s) leading to these measures are not AEs, if the condition(s) was (were) known before the start of study treatment. In the latter case, the condition should be reported as medical history.

Weight gain or loss will not be recorded as an AE. Hyperphagia behaviors and skin picking will not be recorded as AEs; however, any other behaviors may be recorded as AEs based on the Investigator's opinion.

Patients will be monitored throughout the study for AEs. All AEs must be followed until they are resolved or stabilized, or until all attempts to determine resolution of the event are exhausted. The investigator should use his/her discretion in ordering additional tests as necessary to monitor the progress of such events.

Adverse events reported prior to dose administration will be recorded as part of the patient's medical history.

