6.2.7. Pharmacokinetics Assessments

Blood draws for PK sampling will be taken at each visit during the Baseline (Visit 3), Maintenance Period (Visits 6 and 8), and Study Completion/Early Withdrawal (Visit 10).

Whole blood will be obtained in a K₂-EDTA Vacutainer[®] tube for the determination of the plasma levels of CBD and 7-OH-CBD. The blood sample will be obtained prior to study medication dosing.

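### No liver chemistry is scheduled during about 13 weeks of double-blind dosing, so the mandatory liver stopping rules cannot catch a symptom-free ALT/AST rise before Week 13

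*Protocol*

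**What the plan says.** Protocol Section 3.6 makes discontinuation mandatory when any of four liver criteria is reached:

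1. ALT or AST above 8 x ULN.
2. "ALT or AST > 5 x ULN for more than 2 weeks".
3. "ALT or AST > 3 x ULN and (TU>2 x ULN or INR>1.5" (closing bracket omitted).
4. ALT or AST above 3 x ULN together with symptoms such as fatigue, nausea, vomiting or rash, or with eosinophilia.

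On sampling, Section 6.2.5.2 states: "Blood samples for the following serum chemistry assessments will be collected at the Screening (Visit 1), and Study Completion/Early Withdrawal (Visit 10) Visits". The panel contains ALT, AST and total bilirubin, but not INR. Table 1 has a laboratory mark at Week 3, which footnote d explains: "Blood sample for complete blood count (CBC) will be collected at Week 3 (Visit 5"). Section 7.4.1 lists the same blood count, plus PK draws at Weeks 5 and 9, and no chemistry. Section 8.6.4.2 plans laboratory summaries for Screening and Study Completion/Early Withdrawal only. SAP Appendix A repeats the protocol schedule.

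On unscheduled testing, Section 6.2.6.1 says: "The investigator should use their discretion in ordering additional tests as necessary to monitor the progress of such events". The events meant are adverse events.

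**The concern.** A stopping rule based on a laboratory value works only if the value is measured while stopping can still help. Here the rule is mandatory, but the schedule supplies no ALT, AST or bilirubin result during titration or maintenance. A rise without symptoms would go unseen until double-blind treatment ends, and one that resolves before Visit 10 would never be seen.

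The patients are aged 8 to 17. Section 1.5 says they receive the maximum tolerated dose identified in earlier work. Inclusion criterion 8 admits ALT and AST up to 3 x ULN, the level above which criteria 3 and 4 begin to apply. Section 1.6 names the stopping rules among the protections for these patients. Safety is also a secondary objective, and its hepatic part would rest on one post-dose value per patient.

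**Working it through.** The plan states no figure to reproduce. The check counts scheduled samples and sets them against what each criterion needs.

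**Inputs**
- Titration 1 week and maintenance 12 weeks (Protocol 3.1).
- Screening at Week -4 to -2; Visit 10 at Week 13 (Table 1).
- Chemistry at Visit 1 and Visit 10/Early Withdrawal (6.2.5.2; Table 1 footnote d; 7.1; 7.4.2).
- No chemistry in the procedure lists for Visits 2, 3 and 4 (7.2.1, 7.3.1, 7.3.2), Visits 5 to 9 (7.4.1) or Visit 11 (7.6.1).
- Blood already drawn at Week 3 (blood count) and at Weeks 5 and 9 (PK).

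**Time without scheduled chemistry**
- Double-blind dosing before Visit 10: 1 + 12 = 13 weeks (nominally Day 1 to Day 91, so 90 days).
- Screening sample to Week 13: 13 + 2 = 15 to 13 + 4 = 17 weeks. Subtracting the 13 weeks of dosing leaves 2 to 4 weeks before double-blind treatment.
- Scheduled chemistry values between first double-blind dose and Visit 10: 0.
- Scheduled post-dose chemistry values per patient: 1.

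**Each criterion against the scheduled data**

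| Criterion | Needs | Before Visit 10 | At Visit 10/Early Withdrawal |
|---|---|---|---|
| 1. > 8 x ULN | one ALT/AST value | none | can be assessed |
| 2. > 5 x ULN for > 2 weeks | at least two values > 14 days apart | none | cannot be met: one value only |
| 3. > 3 x ULN with TU or INR | ALT/AST plus bilirubin or INR | none | bilirubin branch only, if TU means total bilirubin; no INR scheduled |
| 4. > 3 x ULN with symptoms or eosinophilia | ALT/AST when the sign is present | none | can be assessed if the sign is present then |

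**What a Visit 10 result can still change**

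By Visit 10 the double-blind course is over. For patients who do not enter the long-term study, the remaining dosing is the taper: "40 mg/kg/day dose will be reduced to 30 mg/kg/day for three days, then 30 mg/kg/day will be reduced to 20 mg/kg/day for three days". Dosing stops after that. The taper is 3 + 3 = 6 days from 40 mg/kg/day, or 3 days for a patient already on 30 mg/kg/day (Section 4.1.5). Otherwise the result can affect only entry to the long-term study. An Early Withdrawal sample comes after the decision to stop, and Section 3.4 asks for those evaluations only where possible and reasonable.

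**With chemistry at Weeks 3, 5, 9 and 13**

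Intervals from first dose are 3, 5 - 3 = 2, 9 - 5 = 4 and 13 - 9 = 4 weeks; 3 + 2 + 4 + 4 = 13. The longest unmonitored interval falls from 13 to 4 weeks. Weeks 3 and 5 are nominally exactly 14 days apart, so criterion 2 still needs a repeat-test instruction.

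**The case against.** The strongest reply is that scheduled samples are not the only source of data. Section 6.2.6.1 counts an abnormal laboratory value as a possible adverse event and leaves further tests to the investigator. Physical examination, including abdomen and skin, and adverse event review take place at every visit through Visit 10, about every two weeks during maintenance, with calls on Days 3 and 6. Criterion 4 cannot be applied without an ALT/AST value, so testing on symptoms is arguably implied. A persistence criterion normally relies on repeat tests after a first high value, and INR can be ordered when enzymes are raised. The documents also show no hepatic signal: Section 1.6 lists CYP interaction and immune effects, Section 1.3.3 reports no liver pattern, and chronic liver disease is excluded.

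Part of this stands. The rules are unable to act only as far as scheduled data go, and clinical contact narrows the gap for symptomatic patients. The symptom route is nevertheless weak, because no section requires chemistry when a listed symptom appears. Fatigue, one of those symptoms, was reported in 13% of patients in the open-label cannabidiol study cited in Section 1.3.3, so it may not prompt a liver test. That study used a plant-derived product in epilepsy, however, and fatigue is not among the common events listed for the sponsor's own product, so this point carries little weight. The missing second value and missing INR are best met by a reflex-test instruction, which the plan lacks.

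The reply does not reach the central case. A silent rise produces no adverse event to follow and no first high value to repeat. The lack of a documented hepatic signal does not settle it either, since the sponsor made the rules mandatory.

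**Conclusion.** The concern holds. There are 0 scheduled ALT, AST or bilirubin values in about 13 weeks of double-blind dosing before Visit 10, 1 scheduled post-dose value per patient, and 0 scheduled INR values. Criterion 2 can never be met from scheduled data. The other criteria can be assessed from it only when treatment is ending or has been stopped, and the INR branch of criterion 3 not at all.

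This rests on nominal visit timing and on footnote d, which limits the Week 3 sample to a blood count; Sections 6.2.5 and 7.4.1 agree with it. No rate of liver injury is assumed, and the documents give none for this product. The primary efficacy analysis is not affected. Because a stated safeguard for children at the maximum tolerated dose is largely unable to act as scheduled, and the remedy is cheap, this should be corrected rather than left as a matter of preference.

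**What to change.** - **Sampling.** Add ALT, AST and total bilirubin at Visits 5, 6 and 8 (Weeks 3, 5 and 9) in Protocol 6.2.5.2, 7.4.1 and 8.6.4.2, in Table 1 (marks at Visits 6 and 8, and footnote d), and in SAP Appendix A. SAP Section 7.7.3.1 already summarises laboratory data by visit, with shifts at each scheduled post-baseline visit, so its analysis text needs little change.
- **Triggered testing.** In Section 3.6, require ALT, AST and bilirubin when a criterion 4 symptom appears. Require prompt repeat chemistry plus INR when ALT or AST exceeds 3 x ULN, with repeats continued long enough to judge the 2-week criterion.
- **Wording.** Replace TU in criterion 3 with total bilirubin if that is what is meant; it may be an error in the text extraction.

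**Cost.** A short protocol and SAP amendment, and one serum tube per patient at three visits that already have a blood draw: at most 66 x 3 = 198 tubes with their assays, if all 66 patients attend all three. The PK sample cannot serve, because Section 6.2.7 specifies a K2-EDTA "tube for the determination of the plasma levels of CBD and 7-OH-CBD". Scheduled visits need no extra venepuncture. Repeat chemistry and INR fall only on patients with raised enzymes, and symptom-triggered chemistry only on those with a listed symptom.
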